4.0 Recruitment Methods

4.1 Identification of subjects

Participants will be recruited from Penn State Hershey Medical Center (PSHMC) and University of Southern California (USC) local stroke network. At Penn State, recruitment will include the [name] Laboratory's current database consisting of a large number of current and previous stroke participants, and by Penn State Hershey Medical Center's neurologists including [name], and local stroke support groups/hospitals. At USC, recruitment will include the [name] Laboratory's current database, a database of current and previous stroke survivors at USC, USC's Neurology Department, and local stroke support groups/hospitals. We will also use StudyFinder for recruitment. Participants may also contact researchers directly. Flyers may also be placed in local locations.

4.2 Recruitment process

After identifying potential subject, they will be sent a letter to notify them of the study, unless the participant contacts the lab first. They will be contacted by a study team member by telephone within 2 weeks of sending the letter.

4.3 Recruitment materials

Letter to patient, Flyers
(See StudyFinder page)

4.4 Eligibility/screening of subjects

See StudyFinder page for telephone script.

5.0 Consent Process and Documentation

5.1 Consent Process

5.1.1 Obtaining Informed Consent

5.1.1.1 Timing and Location of Consent

Informed consent will be obtained from all participants at the beginning of the first session at either Hershey Medical Center (Room C2852) or USC, Biophysical Therapy Dept.

5.1.1.2 Coercion or Undue Influence during Consent

To minimize the possibility of coercion or undue influences, each participant will be thoroughly explained the purpose and expectations of the study. The participants will also be made aware that the study is completely voluntary and they can withdraw themselves at any time. In addition, consent will be explained to the patient by a member of the research team who doesn't have any prior relationship with the potential participants.

5.1.2 Waiver or alteration of the informed consent requirement

The study team is requesting a waiver of informed consent to allow for recruitment from clinical schedules and curated databases.

5.2 Consent Documentation

5.2.1 Written Documentation of Consent

Consent will be documented in writing by having the participant sign the informed consent form at the beginning of the first research session, and documents will be kept in a locked filing cabinet (please see consent documents). Participants will receive a paper copy of the signed informed consent document at their first session.

5.2.2 Waiver of Documentation of Consent (Implied consent, Verbal consent, etc.)

The study team is requesting this waiver to allow for telephone screening and scheduling.

5.3 Consent – Other Considerations

5.3.1 Non-English Speaking Subjects

not applicable

5.3.2 Cognitively Impaired Adults

not applicable

5.3.2.1 Capability of Providing Consent

not applicable

5.3.2.2 Adults Unable To Consent

not applicable

5.3.2.3 Assent of Adults Unable to Consent

not applicable

5.3.3 Subjects who are not yet adults (infants, children, teenagers)

not applicable

5.3.3.1 Parental Permission

not applicable

5.3.3.2 Assent of subjects who are not yet adults

not applicable

6.0 HIPAA Research Authorization and/or Waiver or Alteration of Authorization

6.1 Authorization and/or Waiver or Alteration of Authorization for the Uses and Disclosures of PHI

Check all that apply:

- Not applicable, no identifiable protected health information (PHI) is accessed, used or disclosed in this study.** *[Mark all parts of sections 6.2 and 6.3 as not applicable]*
- Authorization will be obtained and documented as part of the consent process.** *[If this is the only box checked, mark sections 6.2 and 6.3 as not applicable]*
- Partial waiver is requested for recruitment purposes only (Check this box if patients' medical records will be accessed to determine eligibility before consent/authorization has been obtained).** *[Complete all parts of sections 6.2 and 6.3]*
- Full waiver is requested for entire research study (e.g., medical record review studies).** *[Complete all parts of sections 6.2 and 6.3]*
- Alteration is requested to waive requirement for written documentation of authorization (verbal authorization will be obtained).** *[Complete all parts of sections 6.2 and 6.3]*

6.2 Waiver or Alteration of Authorization for the Uses and Disclosures of PHI

6.2.1 Access, use or disclosure of PHI representing no more than a minimal risk to the privacy of the individual

6.2.1.1 Plan to protect PHI from improper use or disclosure

Information is included in the "Confidentiality, Privacy and Data Management" section of this protocol.

6.2.1.2 Plan to destroy identifiers or a justification for retaining identifiers

The list linking subject numbers to their PHI will be deleted following publications of study within 2 years of study closing. Any paper copies will be shredded.

6.2.2 Explanation for why the research could not practicably be conducted without access to and use of PHI

In order to identify potential participants, stroke patients' charts must be accessed to screen for inclusion criteria. Because we exclude hundreds of subjects from the stroke database due to exclusion criteria, it would not be practical to contact patients unless they are an appropriate fit for the study. In addition, contact information needs to be obtained.

6.2.3 Explanation for why the research could not practicably be conducted without the waiver or alteration of authorization

Given the number of subjects and the possibility that subjects may no longer be living this research would not be practical without waiver. No clinical information which would be pertinent to the care of individual subjects is expected to result from this study.

6.3 Waiver or alteration of authorization statements of agreement

Protected health information obtained as part of this research will not be reused or disclosed to any other person or entity, except as required by law, for authorized oversight of the research study, or for other permitted uses and disclosures according to federal regulations.

The research team will collect only information essential to the study and in accord with the 'Minimum Necessary' standard (information reasonably necessary to accomplish the objectives of the research) per federal regulations.

Access to the information will be limited, to the greatest extent possible, within the research team. All disclosures or releases of identifiable information granted under this waiver will be accounted for and documented.

7.0 Study Design and Procedures

7.1 Study Design

- Two 20-40-minute components comprise each session, one consists of virtual reality (VR) 'games' that separately target right- and left-hemisphere specific motor deficits, and the next component consists of dexterity training. The order of these sessions will be counterbalanced between subjects.
- The VR component is designed to focus on specific aspects of control that we have previously shown to be deficient in the non-paretic arm of right or left hemisphere damaged stroke patients. For the first 20-30 minutes of training, patients with LHD and RHD will practice tasks adapted to the motor control deficits associated with the damaged hemisphere. LHD patients will practice virtual shuffleboard, which focuses on predictive aspects of trajectory control, while RHD patients will play tracing games that focus on feedback mediated control.
- We then follow this with 30-40 minutes of hemisphere-independent speed and accuracy training of manipulation using a variety of real objects, designed to facilitate generalization and transfer to functional behaviors encountered in the natural environment. In this phase of the session, participants will first engage in mild resistive exercises, using theraputty and theraband, elastic substances designed for resistive exercises of the hand and arm, respectively. After 6 minutes of preparation, all participants will engage in a series of 6 tasks. The order that the tasks are presented will be randomized between sessions for each participant. Each task will be practiced for 4 minutes. The number of items successfully completed in each task will be counted and recorded as a 'target' to beat in the next session, providing motivation for improvement within and between sessions. While most of these tasks are self-explanatory, the

cup-stacking task uses 100 16-ounce disposable plastic cups, which are stacked in rapid sequence. The nuts and bolts task uses 5 varied diameter inverted bolts attached to a wooden base. The participants must pick up and screw on as many nuts as possible in 4 minutes. These tasks were chosen to have no overlap with the components of the JTHFT.

- While our pilot data indicates the effectiveness of this intervention package, it is beyond the scope of this proposal to assess the relative efficacy of its individual components. However, in aim 2, we will determine whether this package of training specifically ameliorated hemisphere-specific movement deficits in RHD and LHD patients. If so, this would suggest that the hemisphere-specificity of the VR training may be important in reducing such deficits.

Comparison Intervention:

- Our comparison intervention is designed to match our experimental intervention in duration and frequency (3X/week for 1 hour over 5 weeks), but using conventional therapeutic activities, based on the best-practices framework for arm recovery post stroke that was developed by an international group of clinicians and researchers in post-stroke rehabilitation [3]. This group, which included occupational therapists, physical therapists, physiatrists, neurologists, and scientists, developed an algorithm for a clinical decision tree which was implemented through a smartphone app, ViaTherapy. In short, recommended therapies are stratified based on research evidence for efficacy, take into account chronicity, potential for reported shoulder pain, and are filtered by co-morbidities such as neglect, cognitive impairment, aphasia, and apraxia.
- To avoid any confounds with the experimental intervention, we exclude any interventions requiring technology that might not be found in a typical community-based rehabilitation clinic, such as robotic rehabilitation, functional electric stimulation, or computer based interfaces. For a typical patient in our study (> 6 months chronicity, no activity limiting shoulder pain, able to partially abduct the shoulder against gravity and partially extend the elbow without gravity, but cannot initiate finger and thumb extension three times within a minute), recommendations include 1) Proximal strength training, 2) Motor imagery and mental practice, 3) Mirror Therapy, using a midsagittal mirror reflecting the non-paretic arm, while the patient attempts bilateral symmetrical forward reaching, and 4) Task specific training, involving reaching toward meaningful objects, with manual assistance as required. The first ten minutes of the 60-minute session will begin with passive range of motion, gentle stretching, and proximal weight bearing, which will help relax spasticity (if present) and prepare the proximal muscles for activity. This will be followed by two of the first 3 recommended therapies (10 minutes each), and then will be followed by 30 minutes of active assisted task-specific reach training. While the specific recommendations may vary slightly based on the decision algorithm, all therapies will begin with 10 minutes of proximal preparation, and all sessions will end with 30 minutes of assisted task-specific reaching of the paretic arm in various directions.
- This study is after the standard care of treatment has been finished or in addition to standard care of treatment, not in place of standard care.

7.2 Study Procedures

7.2.1 Visit 1 (pre-test 1):

Visit 1 (pre-test/screening): subjects will be consented, and then tested using standardized tests including the primary and secondary measures. In addition, the Edinburgh handedness inventory, Confidence in Arm and Hand Movement (CAHM), Multidimensional Scale of Perceived Social Support, NIH stroke scale, tests for comorbidities including testing of grip strength, visual neglect, and apraxia. If they meet criteria for the study, they will be randomly assigned to either the intervention or comparison condition. Tests may be videotaped for scoring and standardization purposes. Participant's names will not be associated with the videotapes. A data safety monitoring board will monitor the study for safety and to minimize risk.

7.2.2 Visit 2 (pre-test 2):

Visit 2 will include the same assessments as visit 1 to establish stability in baseline measures. Participants will also receive an MRI of the brain, which will take about one hour, as long as they are able to have one. The research grade MRI is used for data analysis regarding lesion location and volume. It is standard for studies of this nature to collect this information.

7.2.3 Visit 3-17:

Intervention condition: Two 20-40-minute components comprise each session, one consists of virtual reality (VR) 'games' that separately target right- and left-hemisphere specific motor deficits, and the next component consists of dexterity training. The order of these sessions will be counterbalanced between subjects. The VR component is designed to focus on specific aspects of control that we have previously shown to be deficient in the non-paretic arm of right or left hemisphere damaged stroke patients. For the first 20-30 minutes of training, patients with LHD and RHD will practice tasks adapted to the motor control deficits associated with the damaged hemisphere. LHD patients will practice virtual shuffleboard, which focuses on predictive aspects of trajectory control, while RHD patients will play tracing games that focus on feedback mediated control. We then follow this with 30-40 minutes of hemisphere-independent speed and accuracy training of manipulation using a variety of real objects, designed to facilitate generalization and transfer to functional behaviors encountered in the natural environment. In this phase of the session, participants will first engage in mild resistive exercises, using theraputty and theraband, elastic substances designed for resistive exercises of the hand and arm, respectively. After 6 minutes of preparation, all participants will engage in a series of 6 tasks. The order that the tasks are presented will be randomized between sessions for each participant. Each task will be practiced for 4 minutes. The number of items successfully completed in each task will be counted and recorded as a 'target' to beat in the next session, providing motivation for improvement within and between sessions. These tasks are shown in the flow chart in Figure 5. While most are self-explanatory, the cup-stacking task uses 100 16-ounce disposable plastic cups, which are stacked in rapid sequence. The nuts and bolts task uses 5 varied diameter inverted bolts attached to a wooden base. The participants must pick up and screw on as many nuts as possible in 4 minutes. These tasks were chosen to have no overlap with the components of the JTHFT. While our pilot data indicates the effectiveness of this intervention package, it is beyond the scope of this proposal to assess the relative efficacy of its individual components. However, in aim 2, we will determine whether this package of training specifically ameliorated hemisphere-specific movement deficits in RHD and LHD patients. If so, this would suggest that the hemisphere-specificity of the VR training may be important in reducing such deficits.

Comparison (sham) Intervention: Our comparison intervention is designed to match our experimental intervention in duration and frequency (3X/week for 1 hour over 5 weeks), but using conventional therapeutic activities, based on the best-practices framework for arm recovery post stroke that was developed by an international group of clinicians and researchers in post-stroke rehabilitation [3]. This group, which included occupational therapists, physical therapists, physiatrists, neurologists, and scientists, developed an algorithm for a clinical decision tree which was implemented through a smartphone app, ViaTherapy. In short, recommended therapies are stratified based on research evidence for efficacy, take into account chronicity, potential for reported shoulder pain, and are filtered by co-morbidities such as neglect, cognitive impairment, aphasia, and apraxia. To avoid any confounds with the experimental intervention, we exclude any interventions requiring technology that might not be found in a typical community-based rehabilitation clinic, such as robotic rehabilitation, functional electric stimulation, or computer based interfaces. For a typical patient in our study (> 6 months chronicity, no activity limiting shoulder pain, able to partially abduct the shoulder against gravity and partially extend the elbow without gravity, but cannot initiate finger and thumb extension three times within a minute), recommendations include 1) Proximal strength training, 2) Motor imagery and mental

practice, 3) Mirror Therapy, using a midsagittal mirror reflecting the non-paretic arm, while the patient attempts bilateral symmetrical forward reaching, and 4) Task specific training, involving reaching toward meaningful objects, with manual assistance as required. The first ten minutes of the 60-minute session will begin with passive range of motion, gentle stretching, and proximal weight bearing, which will help relax spasticity (if present) and prepare the proximal muscles for activity. This will be followed by two of the first 3 recommended therapies (10 minutes each), and then will be followed by 30 minutes of active assisted task-specific reach training. While the specific recommendations may vary slightly based on the decision algorithm, all therapies will begin with 10 minutes of proximal preparation, and all sessions will end with 30 minutes of assisted task-specific reaching of the paretic arm in various directions.

Note: sessions may be videotaped for standardization purposes.

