7.2.4 Visit 18: Post test

Visit will include the same assessments as visit 1

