7.3 Duration of Participation

This study will require each participant to attend three 60-minute sessions per week for 5 weeks, as well as 5 separate test (pre and post) sessions, for a total of 20 sessions. If participant misses a session, it will be made up the following week, or by adding it to the end of training sessions. The first two separate pretests take place at visit 1 and 2, one to two weeks apart. The other additional testing sessions take place the visit after the conclusion of therapy sessions, 2 weeks later, and a 6 months following conclusion of therapy sessions.

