8.3 Statistical methods

To assess our intervention, we will fit linear mixed models (LMMs) with single-degree-of-freedom linear contrasts [80] to determine if the data support our predictions (see next section). We will use a linear mixed model with main effects for group (experimental, control) and time (Test) and the group by time interaction simply provides a more flexible approach to the typical analysis of variance (ANOVA) model for a randomized pretest-posttest design. Specifically, LMMs will permit us to account for participant matching with a random cluster effect; and they permit each participant to have her or his initial value (random intercept) and different change patterns across the tests (random coefficients for an underlying piecewise regression). LMMs allow us to use covariates to adjust for any potential confounders. Finally, these models can tolerate missing data on the response, which is not true of the standard ANOVA-based model.

Lesion Reconstruction Methods: [name]'s laboratory personnel will reconstruct stroke lesions from the research grade MRI scans. They will superimpose lesions on each axial slice to identify common areas of lesion overlap associated with damage to the right or left hemisphere and to assess comparability of intrahemispheric lesion location in our two tracks. This grant will not specifically examine intrahemispheric lesion location, but these data will provide pilot data for future studies. To calculate the CST lesion load, we will use the tractography based atlas of human brain connections from the natbrain lab [72]. We will use the MRICron descriptive tool for the calculation of the CST-lesion overlap volume. The binary lesion mask file will be overlaid onto either the left or right binary template CST atlas, and the percentage of CST which overlaps with the lesion is calculated.

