18.3 Subject Enrollment

One statistician will be responsible for randomizing all subjects across both sites and will have communication with researchers weekly.

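### Random assignment is described under Visit 1, before the second baseline at Visit 2, and nothing withholds the allocation or masks assessors until that baseline is complete

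*Combined protocol and SAP*

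**What the plan says.** All references are to the combined protocol and SAP.

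- **7.2.1 (Visit 1).** This visit is both the screening visit and the first pre-test. Consent and the primary and secondary measures come first, and then: "If they meet criteria for the study, they will be randomly assigned to either the intervention or comparison condition". No day is given for drawing or disclosing the assignment.
- **7.2.2 (Visit 2).** "Visit 2 will include the same assessments as visit 1 to establish stability in baseline measures". A brain MRI is added. Allocation is not mentioned.
- **7.3.** "The first two separate pretests take place at visit 1 and 2, one to two weeks apart". A missed session may be made up the following week or added at the end.
- **7.2.3 to 7.2.6.** Training occupies Visits 3 to 17. The first post-test is Visit 18: "Visit will include the same assessments as visit 1". Visits 19 and 20 repeat them again.
- **18.3.** "One statistician will be responsible for randomizing all subjects across both sites and will have communication with researchers weekly".
- **8.3.** The analysis is a "linear mixed model with main effects for group (experimental, control) and time (Test) and the group by time interaction", with a random intercept and random coefficients for a piecewise regression. It adds that "LMMs will permit us to account for participant matching with a random cluster effect".
- **3.3.1 and 3.3.2.** Non-attendance, withdrawal of consent, and a new stroke or disabling disorder are grounds for removal. A removed person with too little data for analysis is replaced.

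**The concern.** The second pre-test exists to show that the baseline is stable. It does so cleanly only if it cannot be affected by knowledge of the arm. If the participant or the assessor knows the assignment at Visit 2, effort, self-report or scoring may differ between arms before any training, and the difference would sit in the reference point for every later comparison. The outcomes are not obviously immune. Section 2.2 describes the Jebsen-Taylor score as a completion time, and the reference list describes the Abilhand as a questionnaire.

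The order also decides how early losses count. Someone who drops out after Visit 1 but before Visit 3 has received no training. If already assigned, that person belongs to a randomised group, and replacing them changes the group. If not yet assigned, they are a screening loss and can be replaced without consequence.

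**Working it through.** The plan gives no figure on this point to reproduce, so the check sets the sections side by side.

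**1. The sequence.** Two pre-tests (Visits 1 and 2), 3 × 5 = 15 training sessions (Visits 3 to 17) and three post-tests (Visits 18 to 20) give 2 + 15 + 3 = 20, which agrees with the total in 7.3. The assignment sentence stands under Visit 1. Read in order, one of the two baselines falls after assignment.

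**2. Is there a rule that delays release?**

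| Section | What it could settle | What it gives |
|---|---|---|
| 7.2.1 | Day of assignment | Eligibility as the condition; no day |
| 7.2.2 | Release after the second pre-test | Nothing on allocation |
| 7.2.3 | Release at the start of training | The content of each arm only |
| 18.3 | Concealment or release point | One statistician, weekly contact |
| 8.3 | Time of matching | Matching is mentioned; when it is done is not |
| 18.4, 18.5 | Oversight of allocation | Safety, adherence and data checks; no release rule |

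None withholds the allocation until Visit 2 is complete.

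**3. Could the allocation arrive before Visit 2?** The pre-tests are 7 to 14 days apart. If the weekly contact is regular, at least one contact falls within that gap. Release before Visit 2 is therefore feasible under the plan's own arrangements. So is release after Visit 2, at a later contact. The text permits either.

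**4. Would masking protect Visit 2 anyway?** Sections 7.2.1, 9.1.4 and 18.2 mention videotapes for scoring and standardisation, but none says that the scorer is unaware of the arm. Nothing says that the assessor or the participant is kept unaware at Visit 2.

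**5. Early losses.** A missed Visit 2 does not by itself remove anyone, because 7.3 allows a make-up. What remains is permanent loss before Visit 3, for example through withdrawn consent, a new stroke or continued non-attendance. In the written order this is a post-randomisation loss, open to replacement under 3.3.2 if too little data exist. With assignment after Visit 2, a loss before release is a screening loss. A loss between release and Visit 3 would still be post-randomisation, but that window is shorter.

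**6. Can an effect be sized?** No. It would need the shift at Visit 2, the shift at the post-tests, and the part each pre-test plays in the contrast. The documents give none of these. The model in 8.3 could use the two pre-tests as a mean, as separate levels of Test, or as a pre-training segment of the piecewise regression. In the last case they could enter a contrast with opposite signs, so no single bias formula covers the plan.

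**The case against.** The strongest reply is that the timing is inferred from placement. The paragraph in 7.2.1 is not a strict chronology: straight after the assignment sentence it turns to videotaping and the safety board. Assignment comes from a central statistician, and release after Visit 2 would fit every sentence. This stands. A reader might infer that the plan chose to measure its second baseline unmasked, or that Visit 2 data were in fact biased. The documents support neither; they show that a safeguard is not written down.

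A second reply is that the change need not reduce net bias. As one illustration, take the mean of the two pre-tests as baseline and a shift d in one arm from knowing the allocation. If d occurs at Visit 2 and equally at unmasked post-tests, the bias is d − d/2 = d/2 in the written order and d after the change. That is correct, and it is why no direction is claimed. But possible cancellation between two unknown shifts is no reason to leave the baseline exposed, and unmasked post-tests are a separate issue.

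Third, a reader might try to count early losses from 8.1. Those figures pool screening failures with attrition and are not split by stage, and 8.1 and 16.2 attach the total of 120 to different annual rates. No useful count follows.

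A reader might also infer that the Visit 2 MRI settles eligibility after assignment. Section 7.2.2 gives its use as analysis of lesion location and volume, so that is not supported.

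**Conclusion.** The point holds as a gap in sequence. Assignment is described before the second baseline, and no section delays its release or masks assessors. A site following the protocol in order could therefore measure Visit 2 outcomes with the arm known, and would carry permanent pre-training losses as post-randomisation losses open to replacement.

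Its extent is structural: one of two baseline visits is exposed, along with the interval between Visit 1 and the start of training. No size or direction of bias and no number of affected participants is claimed. The conclusion assumes that the order of the text guides practice. If the allocation is already released after Visit 2, the fault is only that the protocol does not say so. The case for the change rests on its being almost free, not on a demonstrated error in the treatment comparison.

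**What to change.** Move the assignment sentence from 7.2.1 to the end of 7.2.2, worded for example:

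*After all Visit 2 assessments are complete, participants who meet the criteria are randomised, with any matching done at that point. The statistician releases the assignment only then, and before Visit 3.*

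Section 18.3 should refer to the same release point. Both pre-tests then precede randomisation, and 8.3 can treat them so in the mixed model. Whether they enter as a mean, as separate levels or as a piecewise segment is the statistician's choice and lies outside this point.

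Cost: no extra visits or measurements. Training must be scheduled at slightly shorter notice, because the assignment has to arrive between Visits 2 and 3, and any matching has to wait until Visit 2 is complete. If practice already follows this order, the edit simply documents it. The change does not deal with unmasked post-tests or with replacement of people lost during training; both need their own treatment.
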